6.9 Prohibited medications

Patients are prohibited from receiving the following therapies during the treatment phase of this trial:

- Anti-cancer systemic chemotherapy or biological therapy not part of this protocol
- Immunotherapy not specified in this protocol
- Chemotherapy not specified in this protocol
- Investigational agents other than those listed in this protocol
- Radiation therapy.
 - Radiation therapy to a symptomatic solitary lesion or to the brain may be allowed after consultation with the principal investigator.
 - Radiation to target lesions is prohibited.
- Live vaccines within 30 days prior to the first dose of trial treatment and while participating in the trial. Examples of live vaccines include, but are not limited to, the following: measles, mumps, rubella, chicken pox, yellow fever, rabies, BCG, and typhoid (oral) vaccine. Seasonal influenza vaccines for injection are generally killed virus vaccines and are allowed; however intranasal influenza vaccines (e.g. Flu-Mist®) are live attenuated vaccines, and are not allowed.
- Glucocorticoids for any purpose other than to modulate symptoms from an event of clinical interest of suspected immunologic etiology except for:
 - Dermal, inhaled or intranasal corticosteroids (with minimal systemic absorption) are permitted if the subject is on a stable dose.

- Non-absorbed intra-articular steroid injections are permitted.
 - The use of steroids as prophylactic treatment for subjects with contrast allergies to diagnostic imaging contrast dyes will be permitted.
 - Dexamethasone is permitted as either a pre-medication or as a rescue medication for nausea related to Plinabulin in patients whose nausea is not controlled with a 5HT3 inhibitor alone.
- The Exclusion Criteria describes other medications which are prohibited in this trial.

End of study treatment / Withdrawal procedures

Patients will have completed their participation in the study in the case of:

- Disease progression, except as described in assessment section.
- Unacceptable toxicity
- Need for anticancer therapy not specified in the protocol
- Patient noncompliance with the protocol guidelines.
- Patient lost to follow-up
- Patient choice to withdraw from treatment or withdrawal consent their own request.
- Study closure by Sponsor or Investigator.
- Patients may be withdrawn at any time at the discretion of the Investigator for safety, behavioral, or administrative reasons.

Replacement of patients

Patients who discontinue treatment without receiving study medication will be replaced. No other patients will be replaced

Clinical Study Protocol 9602
Drug Substance: plinabulin
IND: 129799
Protocol v5.1
Date 7/15/2017

Schedule of events

	Screening ¹	Cycle 1		Cycle 2+		Off Study ¹²	Survival follow up
		Day 1 +/- 2 days	Day 15 +/- 2 days	Day 1 +/- 2 days	Day 15 +/- 2 days		
Informed consent ²	X						
Demographics	X						
Medical history	X						
Concurrent meds	X	X	X	X	X	X	
Physical exam	X	X	X	X	X	X	
Adverse event evaluation		X	X	X	X	X	X ¹³
Vital signs ³	X	X ¹⁴	X ¹⁴	X ¹⁴	X ¹⁴	X	
Height, weight ⁴	X	X		X		X	
Performance status	X	X		X		X	
Biopsy ⁵	X			X			
CBC w/differential	X	X		X		X	
Serum chemistry ⁶	X	X		X		X	
Thyroid Function ⁷	X	X		X ⁷			
Serum pregnancy test	X ⁸						
Disease assessment (CT scan) ⁹	X			8 (±1) weeks, starting in C7 12 (±1) weeks ¹⁰		X	
Brain CT or MRI	X ¹¹	As clinically indicated					
Survival assessment							X
Plinabulin		X	X	X	X		
Nivolumab		X	X	X	X		

1: screening evaluations must be performed within 28 days of Cycle 1 Day 1
2: consent must be performed prior to initiation of any screening or study-specific procedures

Clinical Study Protocol 9602
Drug Substance: plinabulin
IND: 129799
Protocol v5.1
Date 7/15/2017

- 3: vital signs should include: temperature, blood pressure, heart rate, and respiratory rate
- 4: height is needed at screening only
- 5: biopsy is mandatory for all subjects if treating physician deems it to be safe and feasible. If treating physician deems biopsy not safe and/or not feasible the subject may still be enrolled if they meet all other inclusion criteria.
- 6: sodium, potassium, chloride, carbon dioxide, creatinine, BUN, glucose, calcium, albumin, total bilirubin, AST, ALT, total protein, and alkaline phosphatase
- 7: TSH, T3, Free T4 will be performed at screening and Day 1 of every ODD cycle
- 8: serum pregnancy test (for women of childbearing potential only). Subjects must use an acceptable method of birth control.
- 9: CT scan scan of known sites of involvement. A prior CT scan that is no more than 28 days before the initiation of treatment may be used.
- 10: disease will be assessed 8 (\pm 1) weeks, after cycle 7 patients will be reimaged every 12 (\pm 1) weeks.
- 11: brain CT or MRI does not need to be repeated if scans were performed within 28 days of C1D1
- 12: off-study evaluation will be performed within 28 days (\pm 7 days) after last dose of study treatment
- 13: adverse events are to be recorded from first administration of investigational drug until 30 days after last dose or until another anti-cancer therapy is initiated.
- 14: vital signs (temperature, blood pressure, heart rate, and respiratory rate) needed prior to (\pm 5 mins) and at the end of every infusion (\pm 5 mins).

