5.1.3 Phase one

The phase one portion of this trial will be a phase-1 dose escalation to determine the safety of plinabulin in combination with nivolumab. For the initial portion of this phase, 3 patients will be enrolled and will receive plinabulin at a dose of 20 mg/m² as well as nivolumab at 240 mg for 1 cycle. Cycles will consist of plinabulin and nivolumab on days 1 and 15 of a 28 day cycle. After these patients receive at least 1 cycle of treatment, and if no DLTs are seen, another cohort of 3 patients will enroll, and be treated with plinabulin at a dose of 30mg/m² and nivolumab at a dose of 240 mg. If there are no DLTs after the first cycle of treatment, the trial will continue with the second phase of the study. Alternatively, if

one or more patients in either cohort experience a DLT the cohort in question will expand to include a total of 6 patients. If no other DLT are seen in these 6 patients, then the next phase of the study will continue. If two or more (2/6) patients in this cohort experienced a DLT, then will stop and an alternative dose level may be considered after further discussion with the sponsor and analysis of the DLT by the study team. If this were to be the case the protocol will be amended. If a delayed DLT occurs (i.e. a DLT that occurs during cycle 2 of treatment) the DLT evaluation period will be extended to include the first 2 cycles of treatment. For definitions of DLT please see section [7.1](#)

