5.1.4 Second Phase

In the second phase of the study patients will receive plinabulin at the MTD identified previously and nivolumab 240 mg on the same day and repeated every 2 weeks. Re-staging studies will be conducted every 8 (+/-1) weeks, after cycle seven scans will be done every 12 (+/-1) weeks. Those who achieve a complete response, partial response, or stable disease will continue on study. Will use RECIST 1.1 criteria to determine response to treatment. Patients with progressive symptomatology and progressive disease seen in imaging studies will be taken off study. To account for pseudo-progression, in the case of progressive disease in the absence of worsening symptomatology, at the discretion of the treating physician, a patient will be allowed to continue receiving treatment for 2 more cycles followed by restaging studies. If progressive disease is confirmed the patient will be taken off study.

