6.6 Tumor Evaluations

CT scan of all known areas of disease with tumor evaluation using RECIST 1.1 and IrRC criteria will be performed every 8 (+/-1) weeks. After 7 cycles of therapy, imaging studies will be performed every 12 (+/- 1) weeks.

- Patients who have a CR, PR, or SD may continue on study per study protocol.
- If progressive disease is documented the patient may remain on study provided:
 - The patient does not have clinical signs or symptoms of tumor progression
 - No decline in ECOG performance status
 - Absence of progressive tumor at critical anatomic sites (i.e. spinal cord compression).
 - Treating physician believes that the patient continues to derive clinical benefit from study treatment
 - Repeat imaging scans should be repeated ≥ 4 weeks (+/- 7 days) after documented progression. If progression is confirmed the subject will be removed from study.

Off Study Visit.

Patients will undergo the following assessments 28 days (+/- 14 days) after last dose of study treatment

- History and physical examination that includes examination of major organ systems, ECOG performance status, weight, vital signs, adverse events assessment
- Laboratory evaluations including:
 - CBC with differential
 - Blood chemistry (sodium, potassium, chloride, carbon dioxide, creatinine, BUN, glucose, calcium, albumin, bilirubin, AST, ALT, total protein, and alkaline phosphatase)

Permitted medications

All treatments that the investigator considers necessary for a subject's welfare may be administered at the discretion of the

investigator in keeping with the community standards of medical care.

If an increase in systolic blood pressure to > 160 mmHg is observed after administration of plinabulin, oral amlodipine 10 mg or an equivalent calcium channel blocker should be administered before each subsequent dose. Increases in systolic blood pressure above 200 mmHg should be managed with nitroprusside or similar regimen per institutional practice.

Dexamethasone may be used as either a pre-medication or as a rescue medication for patients that experience plinabulin-related nausea and vomiting that is not controlled adequately with a 5HT3 agonist (e.g. ondansetron) alone

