7.1 Definition of Dose-Limiting Toxicities (DLT)

A DLT is defined as one of the following adverse events reported during the DLT observation period, if considered to be definitely, probably, or possibly related to either study regimen by the investigator; and fulfills any one of the following criterion using NCI CTCAE Version 4.0:

1. Nonhematologic toxicity as follows:

- a) Grade 4 nonlaboratory toxicity
- b) Grade 3 nonlaboratory toxicity (for example, nausea, vomiting, and diarrhea) lasting >3 days despite optimal supportive care.
- c) Any Grade 3 or Grade 4 laboratory value if:
 - i) Medical intervention is required to treat the patient, or ii)
The abnormality persists for >1 week.

Note: Liver function abnormality: For patients with liver metastasis who begin treatment with Grade 2 aspartate aminotransferase (AST) or alanine amino transferase (ALT), if AST or ALT increases by greater than or equal to 50% relative to baseline and lasts for at least 7 days

2. Hematologic toxicity, as follows:

- a) Grade 4 thrombocytopenia and Grade 4 anemia.
- b) Other grade 4 toxicities lasting ≥ 7 days, or
- c) Grade 3 thrombocytopenia if associated with bleeding and requires platelet transfusion, or
- d) Febrile neutropenia Grade 3 or Grade 4

3. Any grade 5 toxicity

4. Any other significant toxicity deemed by the primary investigator and the sponsor to be dose limiting, for example:

- a) Any toxicity that is possibly related to study treatment that requires the withdrawal of the patient from the study
- b) A delay of > 14 days due to persistent Grade ≥ 2 toxicities in initiating the subsequent cycle, with the exception of Grade 2 fatigue

Any infusion or hypersensitivity reactions occurring during the infusion of the drug are not considered dose-related and therefore will NOT be considered to be a DLT.

Attribution of adverse events.

Unrelated: This relationship suggests that there is no association between the study drug and the reported event.

Unlikely: This relationship suggests that the association between the study drug and the reported event is unlikely.

Possible: This relationship suggests that treatment with the study drug caused or contributed to the AE, ie, the event follows a reasonable temporal

sequence from the time of drug administration or follows a known response pattern to the study drug, but could also have been produced by other factors.

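### The replacement rule has no phase 1 exception and no DLT-evaluable patient is defined, so an early non-toxicity exit leaves a three-patient cohort either short of exposure or without a written next step

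*Combined protocol and SAP*

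**What the plan says.** Section 6.0, under Replacement of patients, gives one rule for the whole trial: "Patients who discontinue treatment without receiving study medication will be replaced. No other patients will be replaced".

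Section 5.1.3 enrols three patients at 20 mg/m2 and then three at 30 mg/m2, with both drugs given on Days 1 and 15 of a 28-day cycle. The step from 20 to 30 mg/m2 reads: "After these patients receive at least 1 cycle of treatment, and if no DLTs are seen, another cohort of 3 patients will enroll". The step from 30 mg/m2 to phase 2 reads: "If there are no DLTs after the first cycle of treatment, the trial will continue with the second phase of the study". The second sentence does not repeat the condition that the cohort's patients receive a cycle. A cohort grows to six only when a DLT is seen.

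Section 7.1 defines a DLT as an event. It does not say how much dosing or follow-up a patient needs in order to count.

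The withdrawal list in Section 6.0 includes exits unconnected with toxicity, among them loss to follow-up, noncompliance and "Patient choice to withdraw from treatment or withdrawal consent their own request".

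Patients who leave are still followed. The Off Study Visit paragraph says: "Patients will undergo the following assessments 28 days (+/- 14 days) after last dose of study treatment". Footnote 13 of the schedule of events has adverse events recorded "until 30 days after last dose or until another anti-cancer therapy is initiated".

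**The concern.** A rule that treats three patients without a DLT as enough to clear a dose presumes that all three were exposed and observed for the DLT period. Refusing to replace dosed patients suits phase 2, where Section 9.2 analyses everyone who receives at least one dose at the MTD. It does not suit a three-patient safety decision.

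Suppose one of three patients takes the Day 1 dose, has no DLT, and leaves before Day 15 by choice. The text then supports two readings and does not choose between them.

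- **Permissive.** There has been no DLT, so the 30 mg/m2 cohort is clear, although fewer than three patients received both cycle-1 doses.
- **Strict.** The cohort must complete cycle 1 first. It cannot, because the leaver may not be replaced and expansion needs a DLT. The wording for the 20 mg/m2 cohort leads to the same dead end.

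Either way the study team would have to improvise the decision, and at 30 mg/m2 that decision opens phase 2.

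**Working it through.** **The plan's own figures.** The protocol gives no operating characteristics for phase 1. Its only design calculation is the Simon design in Section 9.1 (stop at 4 or fewer of 18; reject at 11 or more of 33). Exact two-stage binomial sums give alpha 0.0458, power 0.801, and early-stopping probabilities 0.716 at a 20% response rate and 0.094 at 40%. These agree with the stated .05, 0.8, 0.72 and 0.09. None depends on the phase 1 replacement rule.

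**Inputs from the protocol.** Cohort of 3; two doses in cycle 1; clearance at 0 DLTs in 3, or at 1 in 3 followed by 0 in 3 more.

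**Assumptions, not in the documents.** True cycle-1 DLT rate d; equal hazard per dose; independent exits; a leaver's Day 1 dose is followed as required. A leaver's DLT probability is then h = 1 − (1 − d)^0.5.

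**Exactly one exit among the first three, none in the expansion.**

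- First look, three full exposures: (1 − d)^3
- First look, one exit: (1 − d)^2 (1 − h)
- With expansion, three full exposures: (1 − d)^3 + 3d(1 − d)^2 (1 − d)^3
- With expansion, one exit: (1 − d)^2 (1 − h) + [2d(1 − d)(1 − h) + (1 − d)^2 h] (1 − d)^3

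| d | h | First look: full | One exit | Rise (points) | With expansion: full | One exit | Rise (points) |
|---|---|---|---|---|---|---|---|
| 10% | 0.051 | 0.729 | 0.768 | 3.9 | 0.906 | 0.923 | 1.7 |
| 25% | 0.134 | 0.422 | 0.487 | 6.5 | 0.600 | 0.656 | 5.6 |
| 33% | 0.184 | 0.296 | 0.363 | 6.7 | 0.428 | 0.495 | 6.7 |
| 50% | 0.293 | 0.125 | 0.177 | 5.2 | 0.172 | 0.230 | 5.8 |

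**Averaged over an exit rate w per patient, at d = 1/3.** Each patient's chance of an observed DLT becomes q = d(1 − w) + wh. First-look clearance is (1 − q)^3. Clearance with expansion is (1 − q)^3 + 3q(1 − q)^2 (1 − q)^3. The chance of at least one exit in three is 1 − (1 − w)^3, and of two or more is 3w^2(1 − w) + w^3.

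| w | At least one exit | Two or more | First look | Rise (points) | With expansion | Rise (points) |
|---|---|---|---|---|---|---|
| 0 | 0 | 0 | 0.296 | – | 0.428 | – |
| 5% | 0.143 | 0.007 | 0.306 | 1.0 | 0.443 | 1.5 |
| 10% | 0.271 | 0.028 | 0.317 | 2.0 | 0.457 | 2.9 |
| 20% | 0.488 | 0.104 | 0.338 | 4.2 | 0.487 | 5.9 |

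These clearance figures apply to the permissive reading. On the strict reading nothing is cleared, and the probability of at least one exit is the chance that the initial cohort meets the problem.

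**The case against.** The strongest reply is that Section 5.1.3, read as a whole, means the cohort to complete cycle 1. The 20 mg/m2 sentence says so, and the 30 mg/m2 sentence refers to the period after the first cycle. This is a fair reading, and it rules out stating as fact that the protocol lets 30 mg/m2 clear on fewer than three full exposures. That is only one of two readings. But the strict reading does not remove the problem; it replaces thin exposure with a cohort that cannot proceed.

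Second, the effect may be smaller than shown. The documents report no DLTs at 30 mg/m2 as monotherapy in dose escalation, an MTD not reached, and 7% grade 3 or 4 related events with nivolumab in one cited trial. These do not establish the rate for the combination, but they make low rates plausible, which is why 10% is in the table. The Day 1 dose also has longer than the Day 15 dose to show toxicity within 28 days. If hazard is split 2:1 (an assumption), h at d = 1/3 is 1 − (2/3)^(2/3) = 0.237, and one exit adds 4.3 points at first look, not 6.7. Both points stand.

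Third, there are backstops. An exit for toxicity can be ruled a DLT under Section 7.1, item 4a: "Any toxicity that is possibly related to study treatment that requires the withdrawal of the patient from the study". Scheduled imaging should not normally end cycle 1, since "Re-staging studies will be conducted every 8 (+/-1) weeks". A patient who leaves after Day 15 has had both doses. Toxicity is assessed at each visit, and there is DSMC oversight. These narrow the problem to non-toxicity exits before Day 15, but none says who counts toward clearance, and adverse-event recording may stop when another anti-cancer therapy starts.

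A reader might also infer that a leaver contributes nothing, which would put first-look clearance at 0.444 instead of 0.296 when d = 1/3. The documents do not support that as the general case, because follow-up after the last dose is required. It would apply only to a leaver with no usable follow-up.

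**Conclusion.** The point holds as a minor design weakness. The replacement rule covers both phases, and no DLT-evaluable population is defined. An exit before Day 15 for a non-toxicity reason therefore leaves a cohort either assessed on less exposure than a three-patient rule assumes (permissive reading, 30 mg/m2) or without a permitted next step (strict reading).

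On the permissive reading, one such exit raises first-look clearance by about 4 points at a 10% true DLT rate and by 5 to 7 points at 25 to 50%. Averaged over exit rates of 5 to 20% at a 33% DLT rate, the rise is about 1 to 4 points at first look and 1.5 to 6 with expansion. All DLT and exit rates are assumptions, as is equal hazard per dose.

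It would be wrong to infer that phase 2 is compromised. Its alpha, power and size rest on the Simon rule, which this does not touch.

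**What to change.** In Section 6.0, confine the bar on replacing dosed patients to phase 2. For phase 1, add wording to this effect:

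- A patient without a DLT who misses a cycle-1 dose, or is not followed for 28 days, for reasons unrelated to study drug is not DLT-evaluable and is replaced.
- A patient whose dose is missed, delayed or reduced because of related toxicity stays DLT-evaluable, is reviewed under Section 7.1 item 4, and is not replaced. This prevents replacement from being used to discard bad outcomes.
- A cohort clears only on at least 3 DLT-evaluable patients, or 6 if expanded.
- Replacement applies to the DLT decision only. Any patient dosed at 30 mg/m2 or the MTD stays in the safety data and in the Section 9.2 efficacy population, and counts toward the 18 and the 33.

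Note in Section 9.1 that the total of 39 may rise slightly. With 33 at 30 mg/m2 or the MTD and 6 at 20 mg/m2 (33 + 6 = 39), a replacement in an expanded 20 mg/m2 cohort would exceed it.

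The expected number of replacements per 3 evaluable patients is 3w/(1 − w): 0.16, 0.33 or 0.75 at exit rates of 5, 10 or 20%. For a cohort of six it doubles to 0.32, 0.67 or 1.5. The cost is therefore a protocol wording change, usually less than one extra patient per cohort, and a short delay when a replacement is needed.

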6.0 STUDY CONDUCT AND TRIAL PROCEDURES

Prior to undergoing any study-specific procedure, patients must read and sign the current Institutional Review Board (IRB)-approved informed consent form. Procedures conducted as part of the subject's routine clinical management (e.g., blood count, imaging study) and obtained prior to signing of informed consent may be utilized for screening or baseline purposes provided these procedures are conducted as specified in the protocol.

Screening

Diagnostic or laboratory studies performed exclusively to determine eligibility for this trial must only be done after obtaining written informed consent. Documentation of the informed consent will be maintained in the patient's chart.

Studies or procedures that were performed per standard of care prior to signing the consent form may be used for baseline values if they fall within the screening specified window (see table 6.10).

The screening visit will occur up to 28 days prior to initiating study treatment. The following should be obtained, [see table 6.10](#).

- Medical History
 - Histologic type of lung cancer diagnosis
 - Prior NSCLC treatment history
 - Medical History
 - Subject demographics
- Physical examination
 - Examination of major organ systems
 - ECOG performance status
 - Height, weight, and vital signs (temperature, blood pressure, heart rate, and respiratory rate),
- Laboratory Evaluations should include:
 - CBC with differential
 - Serum chemistry (sodium, potassium, chloride, carbon dioxide, creatinine, BUN, glucose, calcium, albumin, total bilirubin, AST, ALT, total protein, and alkaline phosphatase)
 - Thyroid function (TSH, T3, Free T4)
 - Pregnancy test (serum or urine) for all women of childbearing potential
- CT scan of known sites of involvement (a prior CT scan that is no more than 28 days before the initiation of treatment may be used).
- Brain MRI or CT (prior MRI or CT scan that is no more than 28 days before the initiation of treatment may be used).

Biopsy

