All subjects who sign consent to participate in this trial will undergo a mandatory biopsy prior to the start of treatment and after 1 cycle of treatment. The biopsy is mandatory but the treating physician must deem the biopsy feasible and safe; if the physician feels that the biopsy is not feasible or it is not safe the subject will still be allowed to enroll in trial. The biopsy will take place at baseline after eligibility criteria has been confirmed and after the first cycle. Tumor tissue samples consisting of core needle biopsies of deep tumor tissue or lymph nodes or excisional, incisional, punch, or forceps biopsies of cutaneous, subcutaneous, or mucosal lesions will be obtained. Fine needle aspirates, cell pellets from effusions or bone biopsies are not permitted. Target lesions considered for core needle biopsies should be deemed suitable for retrieval of at least three cores (minimum diameter 18- gauge). The biopsy will be delivered to the laboratory of [name].

Treatment on Days 1 and 15 of each Cycle.

Cycles are defined as 28 days.

- On Days 1 and 15 of each cycle (+/- 2 days), the following will be performed prior to therapy administration:
 - History and physical examination that includes examination of major organ systems, ECOG performance status (Days 1 only), weight (Days 1 only), vital signs, adverse event evaluation
 - Laboratory evaluations (Days 1 only) including:
 - CBC with differential
 - Serum Chemistry (sodium, potassium, chloride, carbon dioxide, creatinine, BUN, glucose, calcium, albumin, bilirubin, AST, ALT, total protein, and alkaline phosphatase)
 - Thyroid function (TSH, T3, Free T4) will be performed on Day 1 of every ODD cycle

Drug Administration

6.1.1 Dose calculation.

Plinabulin doses will be determined by the patient's actual weight on Day 1 of each cycle, Nivolumab doses are fixed at a flat dose of 240mg.

6.1.2 Schedule of administration.

Patients will receive therapy on days 1 and 15 of a 28 day cycle. Therapy will consist of plinabulin administered via intravenous infusion (IV) over 30 minutes (+/- 5 minutes) followed by nivolumab administered via intravenous infusion (IV) over 60 minutes (+/- 10 minutes).

- Cycles one and two require a 1-hr observation period between plinabulin and nivolumab administration. No observation period will be required in subsequent cycles if infusions were tolerated without any infusion reactions.

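### Thyroid function is not scheduled at the Off Study visit, so a patient who stops before Cycle 3 Day 1 has no scheduled post-dose thyroid result

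*Combined protocol and SAP*

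**What the plan says.** The body text and the schedule of events agree on thyroid testing.

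- **Screening.** The thyroid panel is among the screening laboratory tests in section 6.0, and footnote 1 of the schedule says "screening evaluations must be performed within 28 days of Cycle 1 Day 1".
- **On treatment.** Section 6.0, under treatment on Days 1 and 15, says "Thyroid function (TSH, T3, Free T4) will be performed on Day 1 of every ODD cycle". The list containing that item opens with the instruction that "the following will be performed prior to therapy administration". Footnote 7 gives the same rule: "TSH, T3, Free T4 will be performed at screening and Day 1 of every ODD cycle".
- **Off Study visit.** The laboratory list under 6.6 has a blood count with differential and "Blood chemistry (sodium, potassium, chloride, carbon dioxide, creatinine, BUN, glucose, calcium, albumin, bilirubin, AST, ALT, total protein, and alkaline phosphatase". It has no TSH, T3 or free T4, and the Off Study cell of the Thyroid Function row is blank.

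On the calendar, "Cycles are defined as 28 days" and "Patients will receive therapy on days 1 and 15 of a 28 day cycle".

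**The concern.** Safety and tolerability of the combination is the primary objective of phase 1 and a secondary objective of phase 2 (sections 3.0, 5.1.1 and 5.1.2). Sections 7.0 and 8.1 require related adverse events of grade 2 or higher to be recorded. A laboratory abnormality can be recorded only if the test is done.

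Under this schedule the first two thyroid results both precede treatment, and the visit that closes a patient's time on treatment does not repeat the test. The gap is therefore tied to when a patient stops. It is complete for those who leave in the first two cycles, including those who leave because of toxicity. Section 6 replaces only patients who never received study medication, so dosed early stoppers remain in the safety data. What is at stake is ascertainment of thyroid abnormalities in these patients, and the chance to notice one at their last scheduled clinical assessment.

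**Working it through.** The plan states no figure to reproduce. The check is calendar arithmetic on the schedule.

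**Inputs.** Cycle length is 28 days, dosing is on Days 1 and 15, and the visit window is ± 2 days (section 6.0). The Off Study visit is nominally 28 days after the last dose (6.6).

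**Formulas.** Day 1 of cycle k = 1 + 28 × (k − 1). Day 15 of cycle k = 15 + 28 × (k − 1). Off Study = day of last dose + 28.

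**Scheduled panels**

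- Screening: up to 28 days before the first dose.
- Cycle 1 Day 1: day 1, before the dose.
- Cycle 3 Day 1: 1 + 28 × 2 = day 57 (days 55 to 59), before the dose.
- Cycle 5 Day 1: 1 + 28 × 4 = day 113, before the dose.

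**Dosing days before the Cycle 3 panel:** days 1, 15, 29 and 43, four in all.

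**What each stopping point leaves**

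| Last dose | Day | Last scheduled panel | Off Study (nominal) | Days from last panel to Off Study | Scheduled post-dose panels |
|---|---|---|---|---|---|
| Cycle 1 Day 1 | 1 | day 1, pre-dose | 29 | 28 | 0 |
| Cycle 2 Day 15 | 43 | day 1, pre-dose | 71 | 70 | 0 |
| Cycle 4 Day 15 | 99 | day 57, pre-dose | 127 | 70 | 1, none after the last dose |

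In the last row, doses on days 57, 71, 85 and 99 all follow the final panel.

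**Exception.** A patient who attends an odd-cycle Day 1 visit, has the panel drawn and is then not dosed does have a value after the last dose. The statements here concern patients who stop without such a visit.

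**DLT period.** It covers cycle 1, extended to cycles 1 and 2 if a delayed DLT occurs (5.1.3), which is nominally days 1 to 28 or 1 to 56. No post-dose panel is scheduled in either span at nominal timing.

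**Side note.** The Off Study window is ± 14 days in 6.6 and ± 7 days in footnote 12. These should be reconciled, but neither changes the result: for a last dose on day 43 the visit falls on days 57 to 85 or 64 to 78, and neither version includes a thyroid test.

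**The case against.** The schedule is consistent and can be followed as written; this is a design choice. Four points limit what can be claimed.

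**Early stoppers are not necessarily untested.** A reader might infer that they have no post-dose thyroid result at all. The documents do not support that. The nivolumab part of section 7 calls for a full work-up when an immune-related event is suspected, including serological data. Section 7.0 has serious events, and those causing discontinuation, followed until they resolve or stabilise. The Off Study visit includes history, examination and adverse event assessment. Patients who stop for overt toxicity are the ones these provisions reach best. This objection stands, so the claim is limited to scheduled results. Its own limit is that the work-up depends on suspicion and names no thyroid test, so an abnormality without symptoms can still pass unseen.

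**No planned statistic is shown to be biased.** It is tempting to assume an early-stop fraction and a thyroid event rate and to calculate how far the reported rate would be diluted. Neither input is in the documents, the plan reports no thyroid event rate, and the calculation would assume no unscheduled detection and equal risk despite shorter exposure. Section 9.2 summarises Grade 3 or higher toxicity, and no effect on that has been demonstrated. This stands in full.

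**Progression adds an uncertain number.** The first restaging is at week 8 ± 1, and Cycle 3 Day 1 is also at week 8. Only patients removed on a scan before that visit are affected, and 5.1.4 and 6.6 allow some patients with progression to continue.

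**The Cycle 1 Day 1 panel is not simply redundant.** A reader might want to drop it to offset the added test. Blood count and chemistry are also taken at both visits, screening may be 28 days old, and exclusion criterion 15 permits patients with hypothyroidism on replacement. There is good reason to keep it.

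**Conclusion.** The point holds as a gap in scheduled safety testing. A patient who leaves before Cycle 3 Day 1 has two pre-dose thyroid values and no scheduled post-dose value, after as many as four dosing days. A patient who stops later generally has no scheduled value after the last dose. This follows from the schedule alone, at nominal visit timing.

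The consequence is modest: silent laboratory abnormalities in early stoppers can be missed, which weakens ascertainment of related grade 2 or higher events. How many patients this concerns cannot be derived, because the documents give neither the rate of stopping before Cycle 3 nor a thyroid event rate. The response-rate endpoint, the Simon stopping and rejection rules and the Grade 3 or higher summary are not shown to change. It is worth correcting as a cheap improvement, not as a flaw in the trial's inference.

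**What to change.** Add TSH, T3 and free T4 to the Off Study laboratory list in 6.6, and mark the Off Study cell of the Thyroid Function row, extending footnote 7 to match. Keep the Cycle 1 Day 1 panel.

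When thyroid events are summarised, state how many patients had a scheduled post-dose panel. Give this as context and do not restrict the denominator to patients with any post-dose test: symptom-driven tests would then enter while untested patients dropped out, which could push the rate upward.

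The cost is one line of text, one schedule mark and a matching footnote, and one more assay per patient at a visit where blood is already drawn, with no extra visit. The change does not place a panel inside the DLT period for patients who continue; their first scheduled post-dose value remains Cycle 3 Day 1.
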